10.3 End-of-Treatment Phase

10.3.1 Week 49

The following assessments will occur at the end of treatment (\pm 3 days) after the Week 48 dose for all participants or for a participant:

- Review of medical and surgical procedures, concomitant medications, and other treatments; any changes will be noted
- Height and weight
- 12-lead ECG
- Vital signs
- Physical and neurological examination
- Renal ultrasound of kidneys, ureters, and bladder
- Hematology
- Chemistry
- First morning void urinalysis

Note: Analysis of the first morning void urine sample will include urine dipstick protein to be performed at the site.

- Urine cytology (utilizing a urine sample collected on-site)
- Exogenous tracer GFR

Note: This should be done, if possible, per standard of care at the institution.

- Function and strength
 - TTSTAND
 - TTRW
 - NSAA
 - TTCLIMB
 - Hand-held dynamometer
 - 6MWT

- Patient reported outcomes
 - PODCI
 - PARS III Questionnaire
- AE review

10.3.2 Follow-Up Phone Call

Participants will have a phone call conducted with a member of the site study staff, 30 days (\pm 3 days) following the last investigational product infusion, to assess adverse events and medical, surgical, medication, and treatment review. Any AE(s) that is unresolved will be followed up by the site (investigator or designee) for as long as medically indicated. The CRO retains the right to request additional information for any participant with ongoing AEs at the end of the study, if judged necessary.

10.3.3 Unscheduled Visit

If a participant returns to the clinic for a visit outside of the protocol evaluation time points, the visit and any assessments and/or tests performed will be recorded in the source documents and the eCRF as an Unscheduled Visit.

10.3.4 Early Termination or Withdrawal from the Study

A participant (or the legal guardian acting on behalf of the participant) is free to withdraw consent and discontinue participation in the study at any time, without prejudice to further treatment according to standard clinical practice. Study participation may be discontinued at any time at the discretion of the investigator or sponsor. Study participation must be discontinued under the following circumstances:

- Withdrawal of consent by the participant/legal guardian;
- Failure to comply with the protocol;
- Lost-to-follow-up;
- Illness, condition, or procedural complication (including adverse events) affecting the participant's ability to participate or requiring prohibited medication;
- In the Investigator's judgment, it is deemed in the best interest of the participant to discontinue his/her participation in the study;

- The Investigator, sponsor, Data and Safety Monitoring Board (DSMB), and/or regulatory authority terminates the study; or
- Any other reason.

A Participant Completion/Discontinuation eCRF, describing the reason for discontinuation must be completed, for any discontinued or withdrawn participant regardless of reason. If a participant withdraws from the study or if the study is prematurely terminated, the investigator or designee will contact the participant or the participant's legal guardian **within 30 days** after withdrawal or termination to assess any AEs. The investigator will be asked to follow all SAEs until the event returns to baseline or until the investigator determines that follow-up is no longer medically necessary.

Participants who are withdrawn from the study may not re-enter.

The following assessments should be performed at the time of early termination:

- Review of medical and surgical procedures, concomitant medications, and other treatments; any changes will be noted
- Height and weight
- 12-lead ECG
- Vital signs
- Physical and neurological examination
- Renal ultrasound of kidneys, ureters, and bladder
- Urine cytology (utilizing a urine sample collected on-site)
- Anti-dystrophin antibody
- Anti-viltolarsen antibody
- Hematology
- Chemistry
- First morning void urinalysis

Note: Analysis of the first morning void urine sample will include urine dipstick protein to be performed at the site.

- Exogenous tracer GFR

Note: This should be done, if possible, per standard of care at the institution.

- Function and strength
 - TTSTAND
 - TTRW
 - NSAA
 - TTCLIMB
 - Hand-held dynamometer
 - 6MWT
- Patient reported outcomes
 - PODCI
 - PARS III Questionnaire
- AE review

If a participant is lost to follow-up, every reasonable effort must be made by the clinical site personnel to contact the participant and determine the reason for discontinuation/withdrawal (including assessment of any AEs reported by the participant/caregiver). The measures taken to follow-up must be documented in source documents.

10.3.5 Procedures for Early Termination

If a participant withdraws or is removed from the study for any reason, all early termination procedures should be completed per [Table 2](#). Reason for withdrawal, date of the discontinuation, and date of the last dose of investigational product should be recorded in source documents and in the appropriate section of the eCRF. Investigational product assigned to the withdrawn participant may not be assigned to another participant.

The medical monitor should be consulted prior to the withdrawal of the study participant, except in the case of a medical emergency. Written notice (regardless of cause) is to be provided to the medical monitor within 48 hours of the withdrawal. At the time of discontinuation, every effort should be made to ensure all relevant procedures and evaluations scheduled for the final study visit are performed.

10.4 Participant Replacement

Participants will not be replaced.

10.5 Suspension or Termination of Study

If, in the opinion of the medical monitor, clinical observations in the study suggest that it may be unwise to continue, the study may be suspended. The medical monitor will request a DSMB meeting and consult with the sponsor. If the medical monitor, DSMB and sponsor agree that safety concerns warrant termination of the study, the sponsor will terminate the study. A written statement fully documenting the reasons for such a termination will be provided to investigators, IRBs/IECs and regulatory authorities, if required.

NS Pharma has the right to terminate an Investigator's participation in the study and remove all study materials from a clinical site. A written statement will be provided to the investigator, the IRB/IEC, and regulatory authorities, if required.

Possible reasons for termination of the study at a clinical site include, but are not limited to:

- Unsatisfactory enrollment with respect to quantity or quality,
- Inaccurate or incomplete data collection on an ongoing basis,
- Falsification of records, or
- Failure to adhere to the protocol.

If any serious or non-serious adverse events have occurred at such a clinical site, all documentation relating to the event(s) must be obtained.

11 SAFETY PROCEDURES AND PROCESSES

11.1 Definition of an Adverse Event

An AE is any untoward medical occurrence in a participant or clinical investigation participant administered a pharmaceutical product, including control, and which does not necessarily have a causal relationship with treatment. This includes any untoward signs or symptoms experienced by the participant from the time of consent until completion of the study.

AEs may include, but are not limited to:

- Any unfavorable and unintended sign (including an abnormal laboratory finding), symptom, or disease temporally associated with the use of a medicinal product, whether or not considered related to the medicinal product.
- Any new disease or exacerbation of an existing disease.
- Any deterioration in non-protocol-required measurements of laboratory value or other clinical test (e.g., ECG) that results in symptoms, a change in treatment, or discontinuation from investigational product.

Disease signs, symptoms, and/or laboratory abnormalities already existing prior to the use of the product are not considered AEs after treatment, unless they reoccur after the participant has recovered from the preexisting condition or in the opinion of the investigator, they represent a clinically significant exacerbation in intensity or frequency. If clinically significant worsening from baseline is noted, the changes will be documented in the AE source document and the eCRF.

TEAEs are defined as any AE or worsening of an existing condition after initiation of the investigational product and through 30 days after completion of study participation.

Suspected adverse reaction means any AE for which there is a reasonable possibility that the drug caused the AE. For the purposes of investigational new drug (IND) safety reporting, ‘reasonable possibility’ means there is evidence to suggest a causal relationship between the drug and the AE. A suspected adverse reaction implies a lesser degree of certainty about causality than adverse reaction, which means any AE caused by a drug.

An AE or suspected adverse reaction is considered “unexpected” if it is not listed in the investigator’s drug brochure or is not listed at the specificity or severity that has been previously

observed. During the course of the study, the investigator brochure should be updated on an ongoing basis with new important safety information.

11.2 Definition of a Serious Adverse Event

An adverse event is serious when the participant outcome is:

- Death,
- Life-threatening (see below for expanded definition),
- Hospitalization (initial or prolonged),
- Disability or permanent damage (see below for expanded definition),
- Congenital anomaly/birth defect,
- Important medical events that, based upon appropriate medical judgment, may jeopardize the participant and may require medical or surgical intervention to prevent one of the outcomes listed above.

Life-threatening Experience: Any AE that places the participant, in the view of the site investigator, at immediate risk of death from the AE as it occurred, i.e., does not include an AE that, had it occurred in a more severe form, might have caused death.

Any hospital admission with at least one overnight stay will be considered an inpatient hospitalization. However, emergency room visits that do not result in admission to the hospital should be evaluated for one of the other serious outcomes (e.g., life-threatening; required intervention to prevent permanent impairment or damage; other serious medically important event).

Hospitalization for an elective or outpatient procedure will not be considered to be an SAE. However, unexpected complications and/or prolongation of hospitalization that occur during elective or outpatient surgery should be recorded as AEs and assessed for seriousness.

Admission to the hospital for social or situational reasons (e.g., no place to stay, live too far away to come for hospital visits) will not be considered inpatient hospitalizations.

Disability or permanent damage: Any AE that results in a substantial disruption of a participant's ability to conduct normal life functions, i.e., the AE resulted in a significant, persistent or permanent change, impairment, damage or disruption in the participant's body function/structure, physical activities and/or quality of life.

Important medical events that may jeopardize the participant and may require medical or surgical intervention to prevent one of the outcomes listed above: an AE that may not result in death, be life-threatening, or require hospitalization may be considered an SAE when, based upon appropriate medical judgment, it may jeopardize the participant and may require medical or surgical intervention to prevent one of the outcomes listed above.

11.3 Severity

It is the investigator's responsibility to assess the intensity (severity) of an AE.

The severity of the AE will be characterized and recorded as "mild, moderate, severe, life-threatening or death" according to the following definitions: The CTCAE v4.03 guidelines for severity assessments will be used to grade AEs for this trial (available at evs.nci.nih.gov/ftp1/CTCAE/About.html). The CTCAE v4.03 listed guidelines for severity assessment are:

- Mild: Asymptomatic or mild symptoms; clinical or diagnostic observations only or intervention not indicated
- Moderate: Minimal, local or noninvasive intervention indicated or limited age-appropriate instrumental activities of daily living (ADL)
- Severe: Severe or medically significant but not immediately life-threatening; or hospitalization or prolongation of hospitalization indicated; or disabling; or limiting self-care ADL
- Life-threatening: Life-threatening consequences or urgent intervention indicated
- Death: Death related to AE

Note: A severe AE need not be serious, and an SAE need not be severe.

11.4 Relationship

It is the investigator's responsibility to assess the relationship between the investigational product and the adverse event. The degree of "relatedness" of the AE to the investigational product may be described using the following scale:

Not Related

- **Not Related:** No temporal association and other etiologies are likely the cause.
- **Unlikely:** Event or laboratory test abnormality, with a time to drug that makes a relationship improbable (but not impossible). Diseases or other drugs provide plausible explanations.

Related

- **Possible:** Temporal association, but other etiologies are likely the cause. However, involvement of the investigational product cannot be excluded.
- **Probable:** Temporal association, other etiologies are possible but unlikely. The event may respond if the investigational product is discontinued.
- **Definite:** Established temporal association with administration of the investigational product with no other more probable cause. The event should resolve when the investigational product is discontinued and recur on re-challenge.

11.5 Adverse Events of Special Interest

The following events are considered adverse events of special interest based on the route of administration and toxicology profile for viltolarsen:

- Access device complication (for participants with indwelling access devices);
- Urinary protein excretion ≥ 300 mg/day based on a 24-hour urine collection;
- Serum cystatin C $\geq 1.5 \times$ baseline, or serum creatinine $\geq 2 \times$ baseline and ≥ 0.3 mg/dL, confirmed with a repeat test within 1 week of the original results (i.e., meets the cystatin C or creatinine criteria for referral to a pediatric nephrologist described in [Section 11.11.1](#));
- Any confirmed instances of hematuria or other potentially clinically significant abnormalities on urinalysis.

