Viltolarsen was administered once weekly for 26 weeks at dose levels of 0 (vehicle: physiological saline), 50, 150, and 500 mg/kg (51 mice per group) in male CByB6F1-Tg(HRAS)2Jic mice via IV administration with a bolus injection. After the terminal necropsy, macroscopic examinations showed a mass and/or thickening in 1 side of the ureter in 1 mouse at 50 mg/kg, and in 2 mice at 150 mg/kg, and no findings at 500 mg/kg dose group. In subsequent histopathological examinations on these 3 mice, transitional cell carcinomas were noted. Histopathological examination of the ureters for the other mice was conducted and no further tumorigenic changes were identified. Additionally, no treatment-related tumors were noted in any other organs.

The blood concentration of viltolarsen in mice who received 50 mg/kg/week was lower than the blood concentration of viltolarsen expected in human patients who will receive 80 mg/kg/week.

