11.7.2 Adverse Events of Special Interest Reporting

Adverse events of special interest should be promptly recorded in the eCRF so that the DSMB and medical monitor are notified. Such events will be reviewed by the DSMB and medical monitor to enable consideration of implications for other participants.

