11.14 Data and Safety Monitoring Board

It is the responsibility of the DSMB to review data quality, relevant safety data, and AEs for all participants enrolled in the study and to make recommendations to the medical monitor, and sponsor regarding the ongoing conduct and monitoring of the study. Details are provided in the DSMB charter.

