12.6.1 Anthropometrics, Vital Signs, Laboratory Assessments, and ECG

Anthropometrics, vital signs, hematology, chemistry, urinalysis, and ECG results will be summarized by treatment over time using descriptive statistics for continuous outcomes. Actual values and change from Day 1 will be presented. Further, all laboratory abnormalities will be listed.

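### The special-interest event list, said to reflect the toxicology profile, has no entry for urinary-tract neoplasm, renal ultrasound or urine cytology, so such findings lack the prompt DSMB route and a planned by-arm summary

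*Combined protocol and SAP*

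**What the plan says.** Section 11.5 introduces a closed list with the words "The following events are considered adverse events of special interest based on the route of administration and toxicology profile for viltolarsen". It has four entries: access-device complications; 24-hour urinary protein at or above 300 mg/day; confirmed rises in cystatin C or creatinine; and "Any confirmed instances of hematuria or other potentially clinically significant abnormalities on urinalysis".

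Section 11.7.2 attaches a consequence to that list: "Adverse events of special interest should be promptly recorded in the eCRF so that the DSMB and medical monitor are notified". The DSMB and medical monitor then consider what the event implies for other participants.

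The non-clinical summary (Section 2.3.2) describes a 26-week study in transgenic mice with 51 animals per group. Masses or thickening of the ureter were found in three treated animals, and "In subsequent histopathological examinations on these 3 mice, transitional cell carcinomas were noted". It adds: "The blood concentration of viltolarsen in mice who received 50 mg/kg/week was lower than the blood concentration of viltolarsen expected in human patients".

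The schedules (Tables 1 and 2) include ultrasound of kidneys, ureters and bladder at Screening, and urine cytology at the Pre-Infusion Visit. Both are repeated at Weeks 13, 25, 37 and 49 and at early termination, and both are read locally (Sections 9.12 and 9.14.1). Cytology is a safety endpoint in Section 3; ultrasound is not.

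For the analysis, Section 12.6.1 states: "Anthropometrics, vital signs, hematology, chemistry, urinalysis, and ECG results will be summarized by treatment over time", using descriptive statistics for continuous outcomes, with a listing of laboratory abnormalities. It names neither ultrasound nor cytology.

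**The concern.** The list claims to follow the toxicology, and the toxicology includes tumours of the ureter at an exposure below the one expected in the trial. The protocol collects two tests able to show a urinary-tract lesion, but a positive result on either meets no special-interest entry unless the urinalysis is abnormal too.

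What is at stake is the secondary safety objective. In a trial with 37 boys per arm, any such finding would probably be isolated. Its value depends on the DSMB hearing of it promptly and on the arms being set side by side on the results, including those that no investigator reported as an AE.

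**Working it through.** The plan gives no figure on this point to reproduce, so the check is mainly a comparison of sections.

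**1. Does any special-interest entry cover these findings?** The nearest is the hematuria and urinalysis entry. Table 3 lists urine cytology as an item separate from urinalysis, so that entry does not cover it. Ultrasound is not a urine test. A mass, ureteral thickening, new hydronephrosis or atypical cytology without hematuria or another urinalysis abnormality therefore meets no entry.

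**2. Is there a finding-specific rule elsewhere?** Section 11.11.1 sets repeat and referral steps for dipstick protein, protein-to-creatinine ratio, 24-hour protein, cystatin C, creatinine and urinalysis abnormalities. Section 11.12 does so for ECG. Section 9.12 gives ultrasound timing and who reads it, but no reporting rule.

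**3. Which general routes remain?**

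| Route | Section | Prompt DSMB notice stated? |
|---|---|---|
| AE found on review of test results | 9.13, 11.1 | No |
| AE follow-up reported to the medical monitor | 11.10 | No |
| SAE to CRO and sponsor within 24 hours | 11.7.3 | No |
| Medical monitor may suspend the study and request a DSMB meeting | 10.5 | Discretionary |
| General DSMB review of safety data and AEs | 11.14 | No timing given |
| Special-interest event | 11.7.2 | Yes |

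**4. Where would the results be tabulated?** Section 12.4 (baseline) and Section 12.6.1 (over time) name neither test. Section 12.6.2 covers physical examination and AEs, Section 12.6.3 medications, and Section 12.6.3.1 antibodies and PK. Findings reported as AEs enter the TEAE tables by arm. Abnormal cytology may appear in the laboratory listing. Ultrasound is not a laboratory test, so it has no stated listing.

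**5. Volume of data.** There are four scheduled post-baseline time points: 74 × 4 = 296 results per test, or 100 × 4 = 400 at the maximum sample size in Section 12.8. These are tests performed, not events missed.

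**6. The mouse data.** By dose: 1/51 = 2.0%, 2/51 = 3.9% and 0/51. All treated animals: 3/(3 × 51) = 3/153 = 2.0%. The other ureters were examined without further tumours, so vehicle is 0/51. Fisher's exact test of 3/153 against 0/51 gives two-sided p = 0.57.

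**7. How many findings to expect.** The documents give no rate of abnormal findings in boys, so this is an assumed range. The chance of at least one among 37 treated boys is 1 − (1 − p)^37:

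| Assumed p | Chance of at least one |
|---|---|
| 1% | 31% |
| 2% | 53% |
| 5% | 85% |
| 10% | 98% |

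At the lower rates the trial may see one case or none, so how each case is routed matters more than any test between arms.

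**The case against.** The strongest reply is that the protocol already has routes for these findings. A reader might infer that a result is escalated only if someone locally calls it serious. The text does not support that: Section 9.13 counts AEs detected on review of test results, Section 11.10 sends follow-up results to the medical monitor, and Section 11.14 says "It is the responsibility of the DSMB to review data quality, relevant safety data, and AEs for all participants enrolled in the study". A reader might also infer that the arms are not compared at all. That is too strong as well, because reported AEs are tabulated by treatment group under Section 12.6.2. Nor can one say that a finding at Week 13 would stay hidden from the DSMB for the rest of the trial: the frequency of its reviews is left to a charter that is not part of the document.

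The signal itself is open to question. No tumour occurred at the highest dose, the numbers are small, and the protocol does not state that the tumours were attributed to treatment. The remark that other organs showed no treatment-related tumours is at most a hint. Section 12.6.1 is framed around continuous outcomes, so the absence of categorical results there proves little alone. The SAP may add tables; its text is not in the document. Part of the risk discussion in Section 2.4.1 is blacked out and may explain the choice. Basing a list on a toxicology profile also does not promise an entry for every finding.

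All of this limits the consequences. It does not supply an entry in Section 11.5, and Section 12.1 gives the SAP precedence only over data-analysis plans, not over site reporting. Uncertainty about the mouse finding is a reason to collect human findings systematically, since the tests are being done anyway.

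**Conclusion.** The point holds as a bounded reporting gap. Two things are absent from the protocol: prompt DSMB notification of a urinary-tract neoplasm or of an abnormal ultrasound or cytology result as such, and a planned by-arm summary of those results. Ultrasound is also missing from the Section 3 safety endpoints.

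The gap does not touch the primary analysis, the sample size or the type I error, and no effect size can be attached to it. The documents do not show that viltolarsen caused the mouse tumours, nor that any finding in this trial would go unreported.

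The conclusion rests on reading Section 11.5 as a closed list and on the protocol text alone. If the SAP already tabulates both tests by arm, the second half falls away. If the charter requires prompt notice of these findings to the DSMB, the first half is largely met, although sites would still not see it in the protocol. A cheap improvement worth making.

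**What to change.** Reporting changes only; clinical handling stays where the protocol puts it.

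- **Section 11.5:** add (a) any new, potentially clinically significant finding on renal ultrasound, for example a mass, wall thickening, hydronephrosis or hydroureter; and (b) urine cytology reported as atypical, suspicious or malignant. Section 11.7.2 then applies without further edits.
- **Section 3 and the synopsis:** add renal ultrasound to the safety endpoints.
- **Section 12.6.1 and the SAP:** add, for each test, a by-arm table of shift from baseline to worst post-baseline category. Define baseline as the Screening ultrasound and the Pre-Infusion cytology, because neither test is done on Day 1, the reference visit in Section 12.6.1.

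The cost is a few lines of text and two tables from data already scheduled for collection. The downside is some false-positive special-interest reports, since both tests are read locally.
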